Eyetracking data and questionnaire data from the 6-month follow-up visit related to stereotype threat and the digit span task will be analyzed by the University of Southern California (USC) team. All data will be de-identified before being sent to USC for analysis. Each site will upload their de-identified, raw pupillometry data (labeled with subject ID#) to the BU secure Web data repository and from there it will be sent to USC.

Data Analysis

The analytical strategy will focus on comparing A+D+ and A+D- groups on the ADCS-PACC score at 6 months to better identify if non-disclosure itself had an effect on ADCS-PACC performance. Although the primary comparison is not based on the fully randomized groups, it is a comparison of randomized groups in the pre-specified subgroup of A+ subjects, thus controlling for type 1 error. The power calculation is based on the comparison within the subgroup of A+ subjects, so type 2 error is also controlled. Our primary analysis will use a mixed-effects model repeated measures (MMRM)⁵⁷ approach to evaluate the three repeated measures over time. This Intention-to-Treat (ITT) analysis will incorporate information from those who drop out over the 6 months, assuming missing at random, and have better control of type 1 error and power. We will model time as a categorical measure, and the primary outcome will be the estimated difference (contrast) between the two groups at 6 months. As randomization may not be fully successful in balancing confounding factors between the groups (subgroups of the randomized groups), the analysis will also adjust for potentially confounding measures such as sex, age and *APOE* genotype. We will also include the baseline measure of the ADCS-PACC score in one regression model (using the two repeated measures at 6 weeks and 6 months) to allow for differences in cognitive functioning at baseline. We will also consider models that examine change from baseline, with and without adjustment for the baseline measure.

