Primary Analysis 1.1: For this aim we focus on one outcome, ADCS-PACC, and thus use an alpha level of 0.05 to determine statistical significance. First, we will obtain descriptive statistics for those who are in the D+ and D- groups among A+ subjects. Then, we will compare ADCS-PACC scores between D+ and D- groups among A+ subjects using a two-sided test of means. Next, we will compare D+ and D- groups on potential confounders. We will initially consider confounders due to the Covid-19 pandemic (as described below) and then consider other confounders (including age, education, premorbid function, experiences of discrimination). If any are significantly different between the two groups ($p < 0.05$), despite randomization, we will conduct regression analysis adjusting for those confounders that are different. Analyses will be repeated measures (6 wks. and 6 mos.) adjusting for baseline measure at time of randomization. We will focus on 6 month differences, but also check for time-averaged differences between D+ and D- groups. Check ADCS-PACC for normality. If normal, linear regression analysis for repeated measures can be used, specifically a mixed-effects model with repeated measures (MMRM). If not normal, we will use an appropriate transformation to make the distribution more normal. We will also conduct an Intention-to-Treat (ITT) analysis, which will incorporate information from those who drop out over the 6 months, assuming missing at random. This analysis will have better control of type 1 error and power. We will model time as a categorical measure, and the primary outcome will be the estimated difference (contrast) between the two groups (D+ and D-) at 6 months and secondarily the time-averaged difference. We will also apply a model with 3 repeated measures (baseline, 6 wks., 6 months) without adjustment for baseline ADCS-PACC to examine the full trend over time, but this will be a secondary analysis.

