Analysis 1.1 if we do not reach planned sample size: Our plan for this study is to recruit 270 subjects who would be randomized equally to D+ and D- groups. With 10% loss, we expect 120 subjects in each group with about 50% being A+ due to enrichment of *APOE* e4+ participants. Thus, there would be ~60 people in each of the four groups: A+D+, A+D-, A-D+, A-D-. For Aim 1, we powered the study to detect a difference between the A+D+ and A+D- groups. With 60 subjects in each of these two groups, we have 80% power to detect a difference of 1.15 ADCS-PACC points. After pursuing this plan for several years we found that the expected 50% split between A+ and A- participants was too optimistic and in fact we found that the proportion of A+ subjects enrolled in the study was hovering between 25% and 30%, thereby reducing the numbers available for evaluation of Aim 1, the primary research question for the study. In June, 2018, we applied for a supplement to this research project to aid us in attaining needed sample size for Aim 1. We revised our estimated sample size needed for Aim 1 to be 50 in each group (A+D+, A+D-), determining that we could detect a moderate meaningful difference of 1.2451. If we are not able to attain the sample size that we expect (~50 in each group), we will conduct an analysis of the existing sample. If the result is significant, we then had more power than we thought we might; that is, the difference between the two groups was greater than 1.2451. If the difference between the two groups is not significant, we will examine the confidence interval for the difference to obtain a range of estimates of possible differences, given our sample size.

Outliers: Components of the ADCS-PACC and the overall score will be examined for outliers. We will exclude values that are more than 2 standard deviations from expected mean values (based on the literature). In addition, we will consult visit notes and TOMM scores to see if anything unusual might be a factor in the outliers.

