Missing PACC data: Some participants may be missing or have invalid components of the PACC. If missing more than 1 of the PACC components, the participant will be excluded from analysis. If missing 1 or fewer of the PACC components, we will conduct multiple imputation analyses to fill in missing values. Multiple imputation datasets will be derived and analyses will combine results over the imputed datasets, following standard procedures for imputation. For a sensitivity analysis, we will also conduct an analysis excluding these individuals.

Adjusting for Covid-19: The Covid-19 virus impacted the tail end of our study; as a result some visits did not occur when planned. For example, the 6 month visits ranged from 3 months to 14 months. Thus, our primary analysis will adjust for the actual time of the visit. In addition, we will include a dichotomous variable indicating whether the visit occurred after March 15, 2020 or not, since the existence of the Covid-19 virus, a widespread, acute psychological trauma, may have affected the study participants' responses. We will examine the impact of the Covid-19 virus prior to considering other confounders that might impact the results. As a benchmark of comparison, we will also conduct an analysis using the categorical times of the planned visits. Likewise, we will also conduct an analysis that excludes observations after March 15, 2020.

Secondary Hypothesis 1.2: A+D+ participants will have higher scores on scales of subjective memory complaints than A+D- participants.

Secondary Analysis 1.2: Two instruments have measured subjective memory: (1) Metamemory in the Adulthood Questionnaire (108 questions) with two subscores and (2) Memory Functioning Questionnaire (64 questions) with 5 subscores. Thus, these two questionnaires result in 7 different scores. Results from all 7 are summarized in Lineweaver et al paper (2014). Lineweaver et al used two-way MANOVA on all 7 and then proceeded to two-way ANOVA for each of the 7. We plan to conduct this same analytical plan.

Exploratory Hypothesis 1.3: Differences in PACC scores between disclosed and non-disclosed will be larger for African American participants than all other race groups combined.

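### The missing-PACC rule excludes the participant rather than the visit, so as written it discards valid visits and, read literally, the dropouts that the MMRM is meant to keep

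*SAP*

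**What the plan says.** The SAP, Aim 1, paragraph on missing PACC data, has two tiers. With at most one component absent, "If missing 1 or fewer of the PACC components, we will conduct multiple imputation analyses to fill in missing values". Beyond that, "If missing more than 1 of the PACC components, the participant will be excluded from analysis". The paragraph then adds: "For a sensitivity analysis, we will also conduct an analysis excluding these individuals". In context this refers to people with an imputed component, so it takes out more people and restores nobody.

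The analysis that the rule feeds is longitudinal. SAP Primary Analysis 1.1 states: "Analyses will be repeated measures (6 wks. and 6 mos.) adjusting for baseline measure at time of randomization". It also announces an intention-to-treat analysis "which will incorporate information from those who drop out over the 6 months, assuming missing at random". Protocol section VI, Data Analysis, goes further and treats the primary MMRM as that analysis: "This Intention-to-Treat (ITT) analysis will incorporate information from those who drop out over the 6 months, assuming missing at random".

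The SAP paragraph on outliers, which covers the PACC components as well as the total score, says: "We will exclude values that are more than 2 standard deviations from expected mean values". The expected means are to come from the literature. The SAP does not say whether a value removed this way then counts as a missing component.

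**The concern.** An MMRM uses each participant's available visits. A rule that deletes the whole participant because of one bad visit works against it in two ways.

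First, it discards usable data. Someone with two invalid components at 6 weeks and a full battery at 6 months is removed from the 6-month contrast, which is the primary estimate.

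Second, a participant who misses the 6-month visit has every component missing there. Applied literally, the rule removes the people whom the protocol and SAP say are retained. The estimate would then no longer have the protection that a likelihood analysis gives when dropout depends on earlier observed scores. That matters here, because the hypothesis is that disclosure lowers scores and the amyloid-elevated sample is small. Protocol section IX also ends detailed cognitive testing for people who cannot complete it, so missing batteries may be related to cognition.

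Two analysts following the text could build different primary analysis sets after the data are in.

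**Working it through.** **Inputs from the documents.** SD 2.2, difference 1.25, 50 per group, 80% power, 370 enrolled, dropout about 10%, target of 100 completed 6-month visits (protocol, Power Calculation). Two-sided test at 0.05 (SAP, Primary Analysis 1.1). Share amyloid-elevated (A+) 25–30%, and detectable difference 1.2451 (SAP, Analysis 1.1 if planned sample size is not reached).

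**1. The plan's own figure.** Two-sample noncentral t with 50 per group: power for 1.25 is 80.3%, and the difference detectable with 80% power is 1.2449. Both agree with the plan. The completer count also agrees: 370 × 0.90 × 0.30 = 99.9, about 100. So the 50 per group are people who complete the 6-month visit.

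**2. How many dropouts the literal rule could remove.**
- 25% A+: 370 × 0.25 = 92.5; × 0.10 = 9.25
- 30% A+: 370 × 0.30 = 111; × 0.10 = 11.1

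This gives about 9–11 A+ participants. It is a ceiling for lost 6-week data, because it assumes that every dropout attended week 6. The documents give no dropout timing, and a person with no post-baseline PACC adds nothing to the baseline-adjusted model.

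**3. Precision from keeping them.** At 30% A+ there are 55.5 randomised and 50 complete per group. With correlation r between the 6-week and 6-month scores (assumed), the variance of a group's 6-month mean is 2.2² × [(1 − r²)/50 + r²/55.5].

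| r | effective n per group | power for 1.25 (normal approximation) |
|---|---|---|
| completers only | 50.0 | 81.1% |
| 0.3 | 50.5 | 81.4% |
| 0.5 | 51.3 | 82.0% |
| 0.7 | 52.6 | 83.0% |
| 0.9 | 54.4 | 84.2% |

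**4. Bias.** Assumed scenario, by simulation: true difference 0, SD 2.2, 10% dropout in each arm. Dropout is random in D−. In D+ its log-odds rise by 0.5 or 1.0 per SD of lower 6-week score. The table shows the bias of the 6-month D+ minus D− contrast when dropouts are excluded:

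| r | log-odds 0.5 | log-odds 1.0 |
|---|---|---|
| 0.5 | +0.05 | +0.10 |
| 0.7 | +0.08 | +0.14 |
| 0.9 | +0.09 | +0.18 |

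The likelihood estimate that keeps the 6-week scores has a bias of at most 0.003 in absolute value in every case. The positive sign makes D+ look better and so hides a decline. Against the 1.25-unit target, 0.05/1.25 = 4% and 0.18/1.25 = 14%.

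**5. Possible link to the outlier rule.** This applies only if values removed as outliers count as missing. Assume normal components centred on the literature means, between-component correlation 0 to 0.5 and within-person correlation 0.8 across visits. The protocol's list of components (section V, Step 5) can be counted as four or five. The chance of losing two or more components is:

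| components | at one visit | at either post-baseline visit |
|---|---|---|
| four | 1.2–3.0% | 2.1–5.0% |
| five | 1.9–4.2% | 3.3–6.8% |

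**The case against.** The best defence is that the two statements cover different things. The missing-data paragraph opens by speaking of missing or invalid components, which suggests an incomplete battery at an attended visit, while dropout is dealt with in Primary Analysis 1.1. On that reading the dropouts are safe. This is plausible, and it is why the conflict over dropouts is tied here to a literal reading. It does not remove the first problem: even for incomplete batteries at attended visits, the text excludes the participant and not the visit.

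A second defence is that the SAP introduces the intention-to-treat analysis as an additional one, so the main analysis may be something narrower. The missing-data rule exempts neither, and the protocol makes the primary MMRM itself the intention-to-treat analysis.

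Three stronger readings are tempting, and the documents do not support them:
- A reader might infer that power falls from 80% to 76%. That needs 45 per group (noncentral t, 76.0%), which means losing 10% of completers. Dropouts are already outside the 50. The outlier route does not reach 10% in the scenarios above either.
- A reader might infer that the primary analysis becomes a complete-case analysis. It does not strictly do so, because one missing component is imputed.
- A reader might infer that the 2-SD rule feeds this one. The SAP never says so. The percentages in step 5 also rest on assumed normality and on literature means that the documents do not give.

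**Conclusion.** The point holds in a limited form. As written, the rule works at participant level inside a repeated-measures analysis and discards valid visits. Read literally, it also conflicts with the stated use of dropouts' data under missing at random, and nothing else in the documents restores those people.

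The size is probably modest and is not knowable from the documents. At most about 9–11 A+ participants would lose 6-week data through dropout. The number removed for invalid components at one visit is not given. Planned power is not reduced by excluding dropouts alone; what is forgone is 0.3 to 3.1 percentage points of power above the completer figure at r from 0.3 to 0.9. Bias of +0.05 to +0.18 PACC units arises under an assumed mechanism in which dropout depends on 6-week score in one arm only. With no such dependence, this source of bias is absent. The change should be made because it settles who enters the primary analysis and costs almost nothing.

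**What to change.** Replace the exclusion sentence with: *If more than one PACC component is missing at a visit, the composite for that visit is set to missing; all other visits of that participant stay in the MMRM.*

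Keep multiple imputation when one component is missing, and keep participant-level exclusion only as a sensitivity analysis. State whether values removed under the 2-SD rule count as missing components. Since baseline is a covariate in the primary model, also say how a missing baseline composite is handled, because the per-visit rule alone does not settle that.

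The cost is one replaced SAP sentence and two short clarifications, with no new data and no change to sample size. If the authors always meant a per-visit rule, the edit only records it.

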Subjective cognitive measures of the Metamemory in Adulthood (MIA),⁴⁹ and Memory Function Questionnaire (MFQ),⁵⁰ will be administered. The MIA 108-item test is used to describe memory issues and changes relevant to healthy aging, and assess impact of disclosure of perceived cognitive symptoms and abilities.⁴⁹ The MFQ 64-item test reflects subjective appraisals of frequency of forgetting in different situations, the

seriousness of the consequences of forgetting in these situations, comparison of present and past memory functioning, and frequency of memory strategy use; and assesses the impact of disclosure of perceived cognitive symptoms and abilities.⁵⁰

Behavioral health measures obtained at baseline also include: 1) a measure for quality of life, the SF-12 Physical and Mental Health Summary Scale – a 12-item multi-purpose short form (SF) generic measures of health status, and self-rated overall physical and mental health⁵¹; and 2) a measure of how individuals view their future with the Future Time Perspective Scale – a 10-item scale to assess future time perspective as a developmental construct in adults.⁵²

Measures of recall and comprehension, behavioral changes, information sharing and interpersonal relationships, willingness and effort to participate, and cognitive symptoms will be created for this study. Participants will take these created health behavior surveys at baseline and at the 6-week and 6-month follow-up visits (Visits #5 and Visits #6, respectively) to determine the type and frequency of behavior changes in response to learning risk information. Information collected will include assessing health behavior changes, advanced planning, insurance changes (i.e. purchasing or altering long-term care policies), medication changes, willingness to enroll in clinical research, stigma, and tolerance of research risk.

An Emergency Contact Information sheet will be completed by the participant, including two personal emergency contacts and one physician contact. In the event that the participant experiences significant study-related distress, the study team may disclose to an emergency contact that the participant is enrolled in the study. Amyloid status will not be disclosed by the study team.

In addition, Dynamic Experiments for Estimating Preference (DEEP)⁶¹ behavioral assessments will measure participant risk and time preference as presented electronically through various decision-making scenarios.

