Risk Evaluation and Education for Alzheimer's Disease – the Study of Communicating Amyloid Neuroimaging (the REVEAL-SCAN Study)

Statistical Analysis Plan

April 29, 2021

National Institutes of Health/National Institute on Aging: RF1 AG047866

ClinicalTrials.gov Number: NCT02959489

Aim 1: To determine whether disclosure of elevated brain amyloid will bias ADCS-Preclinical Alzheimer Cognitive Composite (ADCS-PACC) test results and subjective memory.

Study Subjects: Those who are Amyloid positive (A+)

Outcome: ADCS-PACC, measured twice (6 wks., 6 mos.) (primary), and subjective memory measures Metamemory in Adulthood Questionnaire and Memory Functioning Questionnaire (secondary), measured twice (6 wks., 6 mos.)

Primary Hypothesis 1.1: At 6 months after disclosure, ADCS-PACC scores will be lower among A+D+ participants than A+D- participants.

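### Secondary Analysis 1.2 tests a directional memory-complaint hypothesis with a non-directional seven-score MANOVA and follow-up ANOVAs, with no multiplicity rule and no stated direction per score

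*SAP*

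**What the plan says.** Secondary Hypothesis 1.2 in the SAP (Aim 1) is directional: "A+D+ participants will have higher scores on scales of subjective memory complaints than A+D- participants". Aim 1 is restricted to amyloid-positive participants, so the disclosure effect is a two-group contrast.

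Secondary Analysis 1.2 takes two subscores from the Metamemory in Adulthood questionnaire and five from the Memory Functioning Questionnaire: "Thus, these two questionnaires result in 7 different scores". It reports that the cited study "used two-way MANOVA on all 7 and then proceeded to two-way ANOVA for each of the 7", and adds: "We plan to conduct this same analytical plan". It does not name the seven scores, say which measure complaints, give an expected sign for any of them, or state an alpha, a time point, a multiplicity rule or the second factor of the two-way layout.

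The protocol (Section V, Step 5, Visit #2) lists among the content of the Memory Function Questionnaire "comparison of present and past memory functioning, and frequency of memory strategy use".

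For the PACC, by contrast, Primary Analysis 1.1 reasons that there is a single outcome and the SAP will "thus use an alpha level of 0.05 to determine statistical significance". No corresponding reasoning is given for seven outcomes.

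**The concern.** The MANOVA null is that all seven means are equal. A change in either direction on any score can reject it, including fewer complaints or a change in something that is not a complaint. Frequency of strategy use is coping behaviour. If disclosure leads people to use more reminders but not to complain more, the MANOVA can reject and the individual ANOVAs follow.

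A preliminary MANOVA limits false positives in the follow-up tests only when no score moves at all. Once one score truly differs, the gate is often open and the remaining true-null scores are each tested at full alpha. With no stated list of complaint scores and no signs, any one of them could then be read as support for Hypothesis 1.2. What is at stake is a spurious secondary claim that learning of elevated amyloid increases memory complaints.

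**Working it through.** **The plan's own figure.** With SD 2.2 (Protocol, Power Calculation) and the SAP's 1.2451 points, 1.2451 / 2.2 = 0.566 SD. With 50 per arm the noncentrality is 0.566 × √(50/2) = 2.83; on 98 df at two-sided 0.05, power is 80.0%. This reproduces the stated figure, but it concerns the PACC. No power or effect size is given for Analysis 1.2.

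**Inputs.** From the SAP: seven scores and 50 per arm. Assumed, because the documents are silent: six complaint scores and one strategy-use score; correlation 0.5 among complaints and 0.2 between strategy use and each complaint; unadjusted 0.05 per ANOVA; disclosure tested as a two-group contrast, which makes the MANOVA a Hotelling T² test on 7 and 92 df.

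**How often the MANOVA rejects when only strategy use moves.** The squared multiple correlation of strategy use with the six complaints is 6 × 0.2² / (1 + 5 × 0.5) = 0.24 / 3.5 = 0.069. For a shift δ, D² = δ² / (1 − 0.069), and the noncentrality is (50/2) × D².
- δ = 0.5: D² = 0.25 / 0.931 = 0.268, noncentrality 6.7, rejection 39%.
- δ = 0.8: D² = 0.64 / 0.931 = 0.687, noncentrality 17.2, rejection 85%.

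**False complaint results.** Simulation, 40,000 trials per row, no true effect on any complaint score:

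| Strategy shift | At least one false complaint, after significant MANOVA | Same, hypothesised direction | ANOVAs always run | Holm over seven, no gate |
|---|---|---|---|---|
| 0 | 3.4% | 1.8% | 20.7% | 3.5% |
| 0.5 SD | 13.3% | 6.8% | 21.0% | 3.9% |
| 0.8 SD | 19.4% | 9.7% | 20.6% | 4.0% |

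As a check, six independent tests would give 1 − 0.95⁶ = 26.5%; correlation lowers this to about 21%. The first row shows that the gate works when nothing moves, and the next two show that it fails when one score does. With complaint correlation between 0.3 and 0.6, the gated figure is 12 to 16% at 0.5 SD and 18 to 23% at 0.8 SD. Holm stays at about 4%.

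**MANOVA against one composite of the six complaint scores.** The SD of the mean of six is √((1 + 5 × 0.5) / 6) = 0.764. Shifted scores rise by 0.4 SD and strategy use is unmoved:

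| Complaint scores shifted | Composite effect | Composite power | MANOVA power |
|---|---|---|---|
| 6 of 6 | 0.400 / 0.764 = 0.524 | 74% | 43% |
| 5 of 6 | 0.333 / 0.764 = 0.436 | 58% | 66% |
| 4 of 6 | 0.267 / 0.764 = 0.349 | 41% | 75% |
| 3 of 6 | 0.200 / 0.764 = 0.262 | 25% | 75% |

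With all six shifted but the strategy correlation at 0.5 instead of 0.2, the MANOVA has 67% against 74%; at 0.6 it has 86% against 74%.

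**Cost of Holm.** For one subscore shifted 0.4 SD, power is 51% at 0.05 and 23% at 0.05/7, Holm's strictest step. If all six complaints shift 0.4 SD, simulated power per score falls from 51% to 28%. The chance that at least one is significant in the predicted direction falls from 87% to 58% (ANOVAs always run).

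**The case against.** The strongest points on the other side are these.

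- The gate is implied by the description of the cited study, not stated as a rule. This is correct. If all seven ANOVAs are reported regardless, a change in strategy use opens nothing. But the false-positive rate is then about 21% whatever strategy use does, so the need for a multiplicity rule is greater.
- The ANOVAs would show that strategy use drove a rejection. They would, but that does not remove a false complaint result beside it.
- Half of the false results run against the hypothesis. This stands, and is why the 7 to 10% figure is given.
- That strategy use is a separate subscore is an inference from the protocol's list of content areas. This stands. The multiplicity problem does not depend on it: it arises whenever any one score moves.
- The hypothesis is secondary in the SAP, exploratory (2.2) in the protocol, and carries no power claim; repeating a published analysis has value. This limits the weight of the point and is a reason to allow the MANOVA to stay.

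A reader might go further and infer that the MANOVA costs 20 to 30 points of power and should give way to a composite. The documents do not support this. They give no effect sizes or correlations for these scores, and Hypothesis 1.2 does not say that all complaint scores rise equally. The loss of about 30 points appears when all do and strategy use is only weakly correlated with them. If three to five of six rise, the composite is worse by about 8 to 49 points.

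**Conclusion.** The concern holds as a mismatch between a directional hypothesis and a non-directional test, and as missing multiplicity control after the MANOVA. Under the stated assumptions, with strategy use alone moving 0.5 to 0.8 SD, at least one false complaint result appears in about 13 to 19% of trials with a MANOVA gate (7 to 10% in the hypothesised direction) and about 21% without one. The correlations, the six-and-one split and the 0.05 level are assumptions; the direction of the conclusion is stable over the range tried.

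It does not show that the MANOVA is generally under-powered, that a composite is generally better, or that a change in strategy use itself creates false complaint findings. Such a change only removes the protection that the gate would otherwise give. The point is a modest one on a secondary analysis, and cheap to settle.

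**What to change.** In Analysis 1.2:

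1. List the seven subscores, mark which measure complaints, and state for each the direction that means more complaints.
2. Apply Holm at 0.05 across the seven disclosure-effect tests. Keep the MANOVA if comparability with the cited study is wanted, and say whether the ANOVAs depend on it. Holm controls the error rate without that gate.
3. Claim Hypothesis 1.2 only from complaint scores that are Holm-significant in the stated direction.
4. Report strategy use separately, as a behaviour and not as a complaint.
5. If wanted, add a standardised complaint composite as a supportive analysis, without describing it as uniformly more powerful.

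This takes SAP wording and minor programming, with no new data. The price is the lower power per subscore shown above. Estimates with 95% confidence intervals for all seven scores would still be reported, so the descriptive comparison with the cited study is kept.

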Analyses of IES as the main secondary outcome and of other measures, will be conducted in a similar fashion. While our main focus for the IES will be upon the contrast between the A+D+ and A-D+ groups, we will also contrast the A+D+ and the D- groups (as long as the A+D- and A-D- exhibit similar outcomes). The D- group may experience increased distress waiting for the disclosure of their imaging, which could reduce our power to explore comparisons between A+D+ and D- groups, although we did not see this occurring in our prior REVEAL studies when participants in the non-disclosure arms were waiting for their genotype data at the end of the study. It will also be of interest to compare the difference between A+D- and A-D- groups, because this comparison would reveal any differences in cognition due to the amyloid burden

itself among participants who do not learn their amyloid status at the fourth visit. We do not expect to find any difference here in only 6 months of follow-up. For Exploratory Aims 1.2 and 2.3, we will examine regression models or MMRM models with interaction terms for race and group to evaluate whether the differences at 6 months between the groups (e.g. A+D+ vs A+D-) are similar for AAs and non-AAs. Point estimates will be considered in addition to confidence intervals and p-values.

For the 6-month follow-up visit digit-span task, we will examine whether working memory performance and pupil dilation responses differ when under high than low threat differentially depending on both disclosure status and amyloid levels.

For the 6-month visit digit-span task, we will examine whether working memory performance and pupil dilation responses differ when under high than low threat differentially depending on both disclosure status and amyloid levels.

Power Calculation

Our objective is to achieve 80% power to detect a difference of moderate effect size (0.4-0.6 SD units) on the primary outcome of ADCS-PACC mean score between the A+D- and A+D+ groups at 6 months.

Assuming a PACC standard deviation of 2.2⁴⁴, 50 individuals per group would provide 80% power to detect a difference of 1.25 PACC units (0.52 SD units) between A+D- and A+D+ at 6 months.

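### The SAP's analysis of the seven MIA and MFQ subjective-memory scores names no baseline covariate, second factor or test visit, and so forgoes precision that the collected Visit 2 scores could supply

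*SAP*

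**What the plan says.** SAP Aim 1 is restricted to A+ participants. Secondary Hypothesis 1.2 states that "A+D+ participants will have higher scores on scales of subjective memory complaints than A+D- participants", without naming a visit. The outcome line gives "subjective memory measures Metamemory in Adulthood Questionnaire and Memory Functioning Questionnaire (secondary), measured twice (6 wks., 6 mos". Secondary Analysis 1.2 counts seven scores (two from the MIA, five from the MFQ), reports that the cited study "used two-way MANOVA on all 7 and then proceeded to two-way ANOVA for each of the 7", and ends: "We plan to conduct this same analytical plan". It gives no other model statement.

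Three other places bear on this:

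- Protocol Section V schedules the MIA and MFQ at Visit 2 (Step 5), before the scan and randomization (Step 7) and disclosure (Step 8). They are repeated at 6 weeks (Step 10) and 6 months (Step 11).
- For the ADCS-PACC, SAP Primary Analysis 1.1 says: "Analyses will be repeated measures (6 wks. and 6 mos.) adjusting for baseline measure at time of randomization".
- Protocol Section VI, Data Analysis, says: "Analyses of IES as the main secondary outcome and of other measures, will be conducted in a similar fashion". The primary methods it refers back to are an MMRM, including a model with the baseline score as covariate.

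The protocol lists this hypothesis as Exploratory Hypothesis 2.2, at 6 months. The SAP lists it as secondary.

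**The concern.** People differ in how much they complain about their memory, and part of that difference is likely to persist over six months. A Visit 2 score can remove that part from the error term. The stated plan does not use it, although it is collected and although the primary outcome in the same aim is handled that way. SAP Analysis 2.1 explains the absence of baseline adjustment for the IES and INI-AD by the absence of a baseline measurement. That reason does not apply to the MIA or MFQ.

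The plan also leaves choices open. Hypothesis 1.2 names one two-level factor, disclosure, while the method is two-way. Amyloid status is constant among A+ participants, so it cannot be the other factor. Two analysts could choose different second factors and different visits and both claim to follow the SAP. At stake are the power of a secondary hypothesis in a trial that struggled to recruit A+ participants, and whether its result can be called pre-specified.

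**Working it through.** **Inputs.** 50 per A+ group, SD 2.2 and 80% power come from Protocol Section VI, Power Calculation. The detectable difference of 1.2451 comes from the SAP paragraph on not reaching the planned sample size. Alpha 0.05 and two-sided testing come from SAP Primary Analysis 1.1. All were set for the ADCS-PACC; the documents give no power figure for the MIA or MFQ. The correlation r between the Visit 2 and follow-up scores is not given and is assumed to lie between 0.3 and 0.8.

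**1. Reproduce the plan's figure.** For a two-sample t-test with 50 per group (98 df), the noncentral t gives a detectable difference of 0.566 SD at 80% power. In PACC units, 0.5659 × 2.2 = 1.245, which agrees with 1.2451. The normal approximation gives (1.960 + 0.842) × √(2/50) × 2.2 = 1.233. The protocol's 0.52 SD does not follow from its own figures (1.25 / 2.2 = 0.568); that is a separate matter and is not used here.

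**2. Add the baseline covariate.** The residual SD becomes SD × √(1 − r²), so the detectable difference is 0.566 × √(1 − r²). Power for a 0.4 SD effect, the lower end of the protocol's moderate range for the PACC, uses noncentrality (0.4 / √(1 − r²)) × √(50/2). The group size that would match the precision of 50 without baseline is 50 × (1 − r²). The one degree of freedom spent on the covariate is ignored.

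| r | 1 − r² | √(1 − r²) | Detectable difference (SD) | Power at 0.4 SD | Equivalent n per group |
|---|---|---|---|---|---|
| no baseline | 1 | 1 | 0.566 | 50.8% | 50 |
| 0.3 | 0.91 | 0.954 | 0.540 | 54.6% | 45.5 |
| 0.5 | 0.75 | 0.866 | 0.490 | 62.8% | 37.5 |
| 0.7 | 0.51 | 0.714 | 0.404 | 79.2% | 25.5 |
| 0.8 | 0.36 | 0.600 | 0.340 | 91.0% | 18.0 |

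These are per-score figures at 0.05, before any adjustment for seven tests.

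**3. Multiplicity.** In the plan as written, the MANOVA is the only step ahead of the seven ANOVAs. If it were dropped and seven tests each run at 0.05, the chance of at least one false positive, if they were independent, would be 1 − 0.95⁷ = 0.302. A replacement model therefore has to carry its own error control.

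**The case against.** The best defence is that the SAP is silent rather than wrong. The outcome line mentions only the two follow-up visits, but it describes the ADCS-PACC in the same way, and the PACC is then adjusted for baseline. That line therefore does not show that baseline is excluded. The protocol's general statement about other measures could be read as supplying the adjustment, and the cited study's own covariates cannot be checked from these documents. This stands in part: what is shown is that no baseline term is stated. But the SAP is later and more specific, and an analyst following Secondary Analysis 1.2 literally would fit none.

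A reader might also infer that the A+ sample has no second factor to offer. The documents do not support that: visit, *APOE* genotype and race can all vary within A+. The factor is unnamed, not unavailable, and leaving it unnamed does not in itself cost precision.

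A reader might infer too that standard errors will be wrong because two visits per person would be treated as independent. That would follow only if visit were the second factor and an ordinary ANOVA were used, and the SAP says neither.

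Finally, the gain depends on r and is small at the low end. Omitting baseline does not bias a randomized comparison, and the hypothesis is secondary. All of that is right, and it limits the point to efficiency and specification.

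**Conclusion.** The point holds as one of lost precision and incomplete specification, not of invalidity. With 50 per group, the unadjusted analysis detects 0.566 SD at 80% power. Using the Visit 2 score brings this to 0.540 SD at r = 0.3, 0.490 at 0.5, 0.404 at 0.7 and 0.340 at 0.8. Power for a 0.4 SD effect goes from 51% to 55% at the low end and to 91% at the high end. The size rests on the assumed r, on reaching 50 per group, and on the SAP being followed as worded. The inconsistency with SAP Primary Analysis 1.1 and with Protocol Section VI, and the missing second factor and test visit, do not depend on r.

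**What to change.** Replace the closing sentence of Secondary Analysis 1.2 with a stated model. Among A+ participants, each of the seven scores is analysed with the Aim 1 repeated-measures model: 6 weeks and 6 months as outcomes; disclosure group, visit and group-by-visit as terms; and that score's Visit 2 value as covariate. The test is the A+D+ versus A+D- contrast at 6 months, the time point in protocol Exploratory Hypothesis 2.2.

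State how the seven tests are controlled: either a global test on the baseline-adjusted scores that must be passed first, or a Holm adjustment across the seven. If a two-way layout is kept for comparability with the cited study, name its second factor and, if that factor is visit, say how the within-person correlation is modelled.

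The cost is a paragraph of SAP text and a few lines of code. No new data are needed, because the Visit 2 scores are already scheduled. Holm would give back some of the per-score power in the table, which should be acknowledged when choosing between the two options.
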